9.1.2.7.3. Work Productivity and Activity Impairment Questionnaire: Psoriasis

The Work Productivity and Activity Impairment-Psoriasis (WPAI-PSO) Questionnaire is a patient-reported instrument developed to measure the impact on work productivity and regular activities attributable to a specific health problem (psoriasis). It contains 6 items that measure: 1) employment status, 2) hours missed from work due to the psoriasis, 3) hours missed from work for other reasons, 4) hours actually worked, 5) degree of health affected-productivity while working, and 6) degree of health affected-productivity in regular unpaid activities. Four scores are calculated from the responses to these 6 items: absenteeism, presenteeism, work productivity loss, and activity impairment. Scores are calculated as impairment percentages (Reilly et al. 1993), with higher numbers indicating greater impairment and less productivity, that is, worse outcomes.

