6.3.3. Modified Baseline Observation Carried Forward (mBOCF)

An mBOCF analysis will be performed on specified continuous efficacy endpoints. For patients discontinuing investigational product due to an AE, the baseline observation for the endpoint will be carried forward to the corresponding visit for all missing observations after the patient discontinued study treatment. For patients discontinuing investigational product for any other reason, the last nonmissing postbaseline observation before discontinuation will be carried forward to the corresponding visit for all missing observations after the patient discontinued. For all patients with sporadically missing observations prior to discontinuation, the last non-missing observation before the sporadically missing observation will be carried forward to the corresponding visit. Randomized patients without at least 1 postbaseline observation will not be included for evaluation with the exception of patients discontinuing study treatment due to an AE.

The mBOCF can be justified based on the composite strategy (ICH E9R1) for handling intercurrent events. It handles the intercurrent event of discontinuing study drug due to an

adverse event by defining the patient as not receiving any benefit from study drug after the event. That is, the patient is defined as reverting back to baseline regardless of any continuing efficacy benefits they may still have received after the event. For other intercurrent events (e.g., rescue treatment and discontinuation due to reasons other than an AE) the while on treatment strategy is applied. That is, the endpoint is defined as the last observed value at or before the visit of interest while the patient was still on study drug.

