		PPASI 75	At least a 75% improvement in PPASI score from baseline.	Missing if baseline or observed value is missing.
		PPASI 100	A 100% improvement in PPASI score from baseline.	Missing if baseline or observed value is missing.
DLQI	
Dermatology Life Quality Index (DLQI): is a validated, dermatology-specific, patient-reported measure that evaluates patient’s health-related QoL. This questionnaire has 10 items that are grouped in 6 domains, including symptoms and feelings, daily activities, leisure, work and school, personal relationships, and treatment. The recall period of this scale is over the “last week.”
 
Response categories and corresponding scores are:
 
 Very much = 3 A lot = 2 A little = 1 Not at all = 0 Not relevant = 0 	DLQI total score	A DLQI total score is calculated by summing all 10 question responses, and has a range of 0 to 30 (less to more impairment) (Finlay and Khan 1994; Basra et al. 2008).	If 2 or more questions are missing, the total score is missing. Note: #7B could be a valid missing while #7A is not “No.” That is, #7 should be considered as 1 question.
		DLQI (0,1)	A DLQI (0,1) response is defined as a postbaseline DLQI total score of 0 or 1. A DLQI total score of 0 to 1 is considered as having no effect on a patient’s HRQoL (Khilji et al. 2002; Hongbo et al. 2005).	Missing if DLQI total score is missing.
		DLQI total score ≥ 5 improvement from baseline	Reduction/Decrease of ≥ 5 points from baseline. A 5-point change from baseline is considered as the minimal clinically important difference threshold.	Missing if baseline or observed value is missing.
		DLQI (0,1) and DLQI total score ≥ 5 improvement from baseline	Patient is a DLQI (0,1) responder and reduction/decrease of ≥ 5 points from baseline.	Missing if baseline or the total score is missing.
		DLQI total score and domain scores change from	Calculated as: observed DLQI (total score or domain scores) – baseline DLQI (total score or domain scores)	Missing if baseline or observed value is missing.

Measure	Description	Variable	Derivation/Comment	Definition of Missing Components
		baseline		
		DLQI symptoms and feelings domain	Sum of responses of questions #1 and #2: #1. How itchy, sore, painful or stinging has your skin been? #2. How embarrassed or self-conscious have you been because of your skin?	If 1 question in a domain is missing, that domain is missing.

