		DLQI daily activities domain	Sum of responses of questions #3 and #4: #3. How much has your skin interfered with you going shopping or looking after your home or garden? #4. How much has your skin influenced the clothes you wear?	If 1 question in a domain is missing, that domain is missing.
		DLQI leisure domain	Sum of responses of questions #5 and #6: #5. How much has your skin affected any social or leisure activities? #6. How much has your skin make it difficult for you to do any sport?	If 1 question in a domain is missing, that domain is missing.
		DLQI work and school domain	Sum of responses of questions question #7A and #7B: #7A. Has your skin prevented you from working or studying? #7B. If No: how much has your skin been a problem at work or studying?	If the answer to question #7A is missing, this domain is missing. If #7A is No, and #7B is missing, this domain is missing.
		DLQI personal relationships domain	Sum of responses of questions #8 and #9: #8. How much has your skin created problems with your partner or any of your close friends or relatives? #9. How much has your skin caused any sexual difficulties?	If 1 question in a domain is missing, that domain is missing.

Measure	Description	Variable	Derivation/Comment	Definition of Missing Components
		DLQI treatment domain	Response of question #10: #10. How much of a problem has the treatment for your skin been, for example, by making your home messy, or by taking up time?	If 1 question in a domain is missing, that domain is missing.
WPAI-PSO	The Work Productivity and Activity Impairment-Psoriasis (WPAI-PSO) Questionnaire is a patient-reported instrument developed to measure the impact on work productivity and regular activities attributable to a specific health problem (psoriasis). It contains 6 items that measure: 1) employment for pay status; 2) hours missed from work due to the psoriasis; 3) hours missed from work for other reasons; 4) hours actually worked; 5) degree of health affected-productivity while working; and 6) degree of health-affected productivity in regular unpaid activities. Greater scores indicate greater impairment (Reilly Associates Health Outcomes Research [WWW]).	Employment Status	Yes/No	Missing if question is missing.
		Absenteeism Score (%)	$\frac{Q2}{(Q2 + Q4)} \times 100$	Missing if Q2 or Q4 are missing. Also missing if Employment Status is No.
		Presenteeism Score (%)	$\frac{Q5}{10} \times 100$	Missing if Q5 is missing. Also missing if Employment Status is No.

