		Work Productivity Loss Score (%)	$\left[\frac{Q2}{Q2 + Q4} + \left(1 - \frac{Q2}{Q2 + Q4} \right) \frac{Q5}{10} \right] \times 100$	Missing if Q2, Q4, or Q5 is missing. Also missing if Employment Status is No.
		Activity Impairment Score (%)	$\frac{Q6}{10} \times 100$	Missing if Q6 is missing. May still be present and non-missing if patient is unemployed.
Rebound	Derived from multiple other measurements mentioned in this table.	Rebound	Defined as having one or more of the following: worsening of psoriasis severity over baseline static Physician’s Global Assessment (sPGA) score, worsening of psoriasis severity over baseline PASI score by 125%, or change in psoriasis phenotype (i.e., from plaque psoriasis to any of guttate, pustular or erythrodermic psoriasis) after randomization to placebo at Week 16.	Missing if baseline or observed value of sPGA or PASI is missing.
		Rebound within 12 Weeks, post re-randomized to placebo	Defined has having rebound for any non-missing visit between Week 16 to (and including) Week 28 (12 weeks post re-randomized to placebo).	Missing if rebound is missing for all Visits, Week 16 to Week 28.

Measure	Description	Variable	Derivation/Comment	Definition of Missing Components

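### The WPAI-PSO Work Productivity Loss rule discards a score that the SAP's own formula fixes at 100% if a patient who worked no hours because of psoriasis leaves Q5 blank

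*SAP*

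**What the plan says.** SAP Section 6.10, Table AMAK.6.5, derives the WPAI-PSO scores from numbered items. Q2 is "hours missed from work due to the psoriasis", Q4 is "hours actually worked" and Q5 is "degree of health affected-productivity while working". Protocol Section 9.1.2.7.3 describes Q5 in the same way: "5) degree of health affected-productivity while working".

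Three of the derivations matter here:

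- **Absenteeism** = 100 × Q2/(Q2+Q4). Rule: "Missing if Q2 or Q4 are missing. Also missing if Employment Status is No".
- **Presenteeism** = 100 × Q5/10. It is missing if Q5 is missing or the patient is not employed.
- **Work Productivity Loss** = 100 × [Q2/(Q2+Q4) + (1 − Q2/(Q2+Q4)) × Q5/10]. Rule: "Missing if Q2, Q4, or Q5 is missing. Also missing if Employment Status is No".

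The last rule has no exception for zero hours worked, and nothing elsewhere in either document supplies one.

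Table AMAK.6.6 analyses change from baseline in patients employed at baseline. Induction uses ANCOVA with mBOCF at Week 16. Maintenance uses MMRM, and also ANCOVA with mBOCF. The protocol's Schedule of Activities collects WPAI-PSO at Weeks 0, 16, 28, 40 and 52 and at early termination. On mBOCF, SAP Section 6.3.3 says: "Randomized patients without at least 1 postbaseline observation will not be included for evaluation". It then makes an exception for patients who stopped study treatment because of an adverse event.

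**The concern.** The missing-data rule and the formula disagree for one kind of patient: employed, with psoriasis-related hours missed and no hours worked. The formula needs only Q2 and Q4 to score this patient, but the rule also demands Q5. Q5 asks about productivity during work, and this patient did no work, so a blank answer is plausible.

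Two features make this more than untidy wording. First, the loss depends on the outcome, because only patients at the top of the scale can be affected. Second, the SAP treats comparable cases differently. Absenteeism for the same patient is scored 100%. In the same table, DLQI item 7B may be legitimately blank when item 7A makes it inapplicable, and Activity Impairment is kept for patients without a job. WPAI-PSO Q5 has no such provision.

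At stake is whether observed worst-case values enter the analysis of Work Productivity Loss, which is named among the Other Secondary endpoints.

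**Working it through.** There is no plan figure to reproduce. The check evaluates the SAP's formula and then traces what happens to a missing score.

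**1. Does Q5 matter when no hours are worked?** Put Q4 = 0 and Q2 > 0. Then Q2/(Q2+Q4) = 1, the weight on Q5/10 is 1 − 1 = 0, and the score is 100 × (1 + 0) = 100.

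| Q2 | Q4 | Q5 = 0 | Q5 = 5 | Q5 = 10 |
|---|---|---|---|---|
| 1 | 0 | 100 | 100 | 100 |
| 8 | 0 | 100 | 100 | 100 |
| 40 | 0 | 100 | 100 | 100 |
| 38 | 2 | 95 | 97.5 | 100 |
| 0 | 40 | 0 | 50 | 100 |

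The first three rows do not depend on Q5. Once any hours are worked, Q5 is needed, so the rule is right there. With Q2 = Q4 = 0 the ratio is 0/0, a case the SAP does not address.

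**2. What happens if Q5 is blank in the first three rows?**

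- *At baseline.* There is no baseline score, so no change from baseline can be formed.
- *At Week 16, induction analysis.* If there is no other post-baseline score, the mBOCF rule excludes the patient, unless treatment was stopped for an adverse event, in which case baseline is carried forward. If the sentence in Section 6.3.3 on sporadic gaps were read as allowing baseline to be carried forward for others too, the 100% would still be replaced by a different value.
- *At a maintenance visit.* MMRM omits that visit, and mBOCF substitutes an earlier value for the 100%. The patient stays in the analysis.

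**3. How far could a group mean move?** Let s be the share of employed patients in an arm at 100% with Q5 blank, and m the mean of the rest. The full mean is 100s + (1 − s)m and the reported mean is m, so the understatement is s × (100 − m). Neither input is in the documents. The assumed ranges are s = 0.5% to 5% and m = 10 to 40.

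| s | m = 10 | m = 20 | m = 40 |
|---|---|---|---|
| 0.5% | 0.45 | 0.40 | 0.30 |
| 1% | 0.9 | 0.8 | 0.6 |
| 2% | 1.8 | 1.6 | 1.2 |
| 5% | 4.5 | 4.0 | 3.0 |

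With 100 placebo patients planned (Protocol Section 5.2), 1% to 2% is at most 1 to 2 people, and fewer once the analysis is limited to the employed.

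**4. Does that give the bias in the treatment effect?** No. The table concerns an arm's mean score at one visit, while the analysed quantity is baseline-adjusted change. Three invented patients show why the sign is open:

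- Baseline 100, Week 16 score 0: losing this patient removes a change of 0 − 100 = −100, an improvement.
- Baseline 20, Week 16 score 100: losing this patient removes a change of 100 − 20 = +80, a worsening.
- 100 at both visits: losing this patient removes a change of 0.

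The net effect depends on how such patients split by arm and visit.

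**The case against.** The strongest objection is that the decisive premise is not in the documents. They paraphrase Q5 but do not reproduce the questionnaire, a skip instruction or the behaviour of the electronic form. If the patient enters any value for Q5, the score computes to 100% and nothing is lost. This stands, and the point has to be conditional. A reader might infer that the rule removes every patient who missed all work. The documents do not support that.

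A reader might also infer that an affected patient always drops out of the analysis. That goes too far as well: there is the adverse-event exception, an early termination assessment, and three further scheduled assessments in maintenance. Nor do the documents support a claim that the treatment effect is diluted. That would need total work loss at Week 16 to persist more often on placebo, which is an assumption, and losing baseline scores can act differently.

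It can also be said that requiring every component is the SAP's usual convention, as for PASI, PSS, PSSI and PPASI. That is true, but those components all have a zero anchor that is the correct entry when nothing is present. Q5 has no natural answer when no work was done.

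Finally, Absenteeism still records the total absence, and re-randomized patients enter maintenance as PASI 90 responders, so such absence should be rarer there. Both points reduce the consequence. Neither reconciles the rule with the formula.

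**Conclusion.** The inconsistency is real: for an employed patient with Q4 = 0 and Q2 > 0, the SAP can set to missing a score that its own formula fixes at 100%. Whether any data are lost depends on Q5 being blank, which is inferred from its wording and not shown.

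The consequence is limited. The number affected is not given and is probably small. The range of 0.3 to 4.5 points for a group mean rests wholly on assumed inputs and is not an estimate of bias in the treatment difference, whose direction is undetermined. Primary and major secondary endpoints are untouched, because the multiplicity procedure in SAP Section 6.5 does not cover this score. The Presenteeism rule is correct, because that score is Q5 itself. This is a low-priority correction, worth making because the value is already known and needs no imputation.

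**What to change.** Replace the missing-data rule for Work Productivity Loss in Table AMAK.6.5 with the following:

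- Missing if Q2 or Q4 is missing, or if Q5 is missing while Q4 > 0.
- If Q4 = 0 and Q2 > 0, the score is 100%, whether or not Q5 was answered.
- If Q2 = Q4 = 0, the score stays missing.
- The employment condition and the Presenteeism rule stay as they are.

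The cost is one derivation line and a small programming change, with no new data. It should be settled before the unblinded analysis of this endpoint. If that has passed, SAP Section 6.1 allows a change that does not alter a principal feature of the protocol to be described and justified in the clinical study report. If no patient has Q4 = 0, Q2 > 0 and a blank Q5, the results do not change.

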Abbreviations: BP = blood pressure; BSA = body surface area; conc = concentration; C-SSRS = Columbia–Suicide Severity Rating Scale; DLQI = Dermatology Life Quality Index; DNA = deoxyribonucleic acid; ECG = electrocardiogram; EQ-5D-5L-PSO = European Quality of Life–5 Dimensions–5 Levels–Psoriasis; ETV = early termination visit; FSH = follicle stimulating hormone; HBcAb = anti-hepatitis B core antibody; HBsAb = hepatitis B surface antibody; HBsAg = hepatitis B surface antigen; HBV = hepatitis B virus; HCV = hepatitis C virus; HIV = human immunodeficiency virus; hsCRP = high-sensitivity C-reactive protein; IL-19 = interleukin-19; IP = investigational product; LV = last study visit; miri = mirikizumab; NAPSI = Nail Psoriasis Severity Index; PASI = Psoriasis Area and Severity Index; PatGA = Patient’s Global Assessment of Psoriasis; PK = pharmacokinetic; PPASI = Palmoplantar Psoriasis Severity Index; PPD = purified protein derivative (skin test); PSS = Psoriasis Symptoms Scale; PSSI = Psoriasis Scalp Severity Index; QIDS-SR16 = 16-item Quick Inventory of Depressive Symptomatology; RNA = ribonucleic acid; SF-36 = Medical Outcomes Study 36-Item Short Form Health Survey; sPGA = static Physician’s Global Assessment; Suppl. = supplement; TB = tuberculosis; temp = temperature; TSQM = Treatment Satisfaction Questionnaire for Medication; V = visit; W = weeks; WCBP = women of childbearing potential; WPAI-PSO = Work Productivity and Activity Impairment Questionnaire: Psoriasis.

- a All activities should be completed prior to any study dose administration, unless otherwise stated.
- b Visit 1 procedures may be conducted over more than 1 day, as long as all tasks are completed within the allowable visit tolerance (at least 3 days should be allowed for receipt of laboratory test results).
- c One complete physical examination (excluding pelvic or rectal examinations) to include heart, lungs, peripheral lymph nodes, and abdomen, and visual examination of all skin areas (including genitalia and breast areas) will be performed at screening. All physical examinations throughout the study should include a symptom-directed evaluation as well as examination of heart, lungs, peripheral lymph nodes, and abdomen, and visual examination of all skin areas (including genitalia and breast areas).

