 - The patient develops a malignancy (Note: patients may be allowed to continue if they develop no more than 2 non-melanoma skin cancers during the study).
 - Any patient who has a change in disease phenotype at any time (for example, a change to pustular psoriasis).
 - If the patient remains at or above their baseline sPGA score at Week 16 (Visit 7) and Week 24 (Visit 9), or remains at or above their baseline PASI score at Week 16 (Visit 7) and Week 24 (Visit 9).
 - It is recommended that the patient be assessed by an appropriately trained professional to assist in deciding whether the patient is to be discontinued from study treatment and the study if:
 - i. The patient, at any time during the study, scores a 3 for Item 12 (Thoughts of Death or Suicide) on the 16-item Quick Inventory of Depressive Symptomatology (QIDS-SR16);

OR

- ii. Develops active suicidal ideation with some intent to act with or without a specific plan (“yes” to question 4 or 5 on the “Suicidal Ideation” portion of the C-SSRS);
OR
- iii. Develops suicide-related behaviors as recorded on the C-SSRS.
 - The patient develops active TB or HIV/AIDS during the study.
 - The patient becomes HBV DNA or HCV RNA positive. The patient should be referred to a specialist physician (see Sections 8.1.2 and 9.4.5.4 for HBV, and Section 9.4.5.5 for HCV).
- Patients will also be permanently discontinued from study drug, complete Post-Treatment Follow-up, and then permanently discontinued from the study in the following circumstances:
 - Enrollment in any other clinical study involving an investigational product or enrollment in any other type of medical research judged not to be scientifically or medically compatible with this study
 - Participation in the study needs to be stopped for medical, safety, regulatory, or other reasons consistent with applicable laws, regulations, and GCP
 - Investigator decision
 - The investigator decides that the patient should be discontinued from the study
 - If the patient, for any reason, requires treatment with another therapeutic agent that has been demonstrated to be effective for treatment of the study indication, discontinuation from the study occurs prior to introduction of the new agent

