- Patients who were responders to mirikizumab in the blinded Induction Period (responder definition is PASI 90 at Week 16) will be re-randomized 1:1:1 to 250 mg mirikizumab once every 8 weeks (Q8W), 125 mg mirikizumab Q8W, or placebo Q8W, according to their randomized treatment assignment at Week 16. Patients who relapse during the blinded Maintenance Period (see relapse criterion defined in [Table AMAK.6.5](#)) will remain on, or will be switched to, 250 mg mirikizumab for the remainder of the study and will be monitored for recapture of efficacy response. These patients will begin retreatment with mirikizumab at the visit at which relapse is identified and will receive another mirikizumab treatment at the next visit 4 weeks later. Subsequent mirikizumab treatments will be given at Q8W intervals.
- Patients who received placebo in the blinded Induction Period who are responders at Week 16 (Visit 7) will continue to receive placebo during the Maintenance Period until relapse.
- Patients who were not responders to mirikizumab in the blinded Induction Period will receive 250 mg mirikizumab Q8W. Continued blinded treatment for nonresponders is provided so that partial or slow responders may remain in the study beyond Week 16, thus, maintaining the study blind while patients continue to receive potentially beneficial longer-term treatment with mirikizumab.

- Patients who received placebo in the blinded Induction Period who are nonresponders at Week 16 (Visit 7) will receive 250 mg mirikizumab Q4W for Weeks 16 through 32 and mirikizumab treatments Q8W, thereafter.

At Week 52, patients may enter the long-term extension study, I6T-MC-AMAH (AMAH), or discontinue study treatment and complete Study AMAK's 12-week Post-Treatment Follow-Up Period. Patients who discontinue the study will stop treatment and continue to the ETV and then complete the 12-week Post-Treatment Follow-Up Period.

Post-Treatment Follow-Up Period (12 Weeks): Patients who do not enroll into Study AMAH or who discontinue early from study treatment in Study AMAK will complete the Post-Treatment Follow-Up Period (Visit [V] 801 and V802) of Study AMAK.

Abbreviations: LV = last study visit; miri = mirikizumab; Q4W = every 4 weeks; Q8W = every 8 weeks; V = visit; W = week; w = weeks.

Note: Randomizations occur at Week 0 and Week 16.

* Option to enter Study AMAH or to enter the Post-Treatment Follow-Up Period.

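### One component is enough for rebound, yet the SAP sets rebound to missing when sPGA or PASI is missing; with Week 16 in the window, such patients normally count as rebound-free

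*SAP*

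**What the plan says.** Three entries in the SAP govern this endpoint.

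- **Definition (Table AMAK.6.5, Rebound).** The derivation opens "Defined as having one or more of the following" and lists sPGA worse than baseline, PASI worse than baseline by a stated margin, and a change of phenotype. It closes with the qualifier "after randomization to placebo at Week 16". The missing-components column for the same row says "Missing if baseline or observed value of sPGA or PASI is missing".
- **12-week variable (same table, next row).** "Defined has having rebound for any non-missing visit between Week 16 to (and including) Week 28 (12 weeks post re-randomized to placebo"). It is "Missing if rebound is missing for all Visits, Week 16 to Week 28".
- **Analysis (Table AMAK.6.6).** Rebound within 12 weeks is summarized descriptively, as observed, in the Re-randomized Maintenance ITT population. SAP Section 6.3.4 says that as-observed summaries use only patients who are completers at the visit.

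Three further provisions matter. SAP Section 5 sets the entry condition for withdrawal: "Patients who were responders to mirikizumab in the blinded Induction Period (responder definition is PASI 90 at Week 16) will be re-randomized 1:1:1". Footnote a of the Schedule of Activities (Protocol Section 2) says "All activities should be completed prior to any study dose administration, unless otherwise stated". Protocol Section 8.2 lists among its reasons for stopping treatment and leaving the study "Any patient who has a change in disease phenotype at any time".

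**The concern.** When one positive component is enough, a single observed positive settles the answer, and nothing missing elsewhere can reverse it. Missing data matter only when no component is positive and at least one is unknown. The SAP rule ignores this distinction.

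The window adds a second problem. Week 16 is the re-randomization visit and is assessed before the first withdrawal-period injection, so it carries no information about what happens after withdrawal. As it sits inside the window and is nearly always scored, it supplies a non-missing *no* for patients who have no other usable visit.

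Both rules push the reported incidence down. Rebound is a withdrawal-risk outcome in a group of about 93, where single cases are visible in the rate.

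**Working it through.** **1. Denominator.** SAP Section 5.1 assumes 400 patients on mirikizumab in induction, 70% of them re-randomized, in a 1:1:1 ratio: 400 × 0.70 / 3 = 93.3. This reproduces the plan's figure of approximately 93 per group. The documents give no expected rebound rate and no expected dropout between Weeks 16 and 28, so the counts in steps 4 and 5 are assumptions.

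**2. Visit level.** Let sPGA and PASI each be positive, negative or missing, and phenotype change be yes or no.

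- All patterns: 3 × 3 × 2 = 18.
- sPGA or PASI missing: 5 of the 9 sPGA-by-PASI pairs, times 2 = 10. The SAP sets all 10 to missing.
- Of these 10, an observed positive is already present in 5 (phenotype change) + 1 (sPGA positive, PASI missing) + 1 (PASI positive, sPGA missing) = 7.
- Only 10 − 7 = 3 are truly undetermined.

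These are counts of logical patterns, not probabilities. One route into them is easy to overlook. Table AMAK.6.5 leaves PASI uncalculated if any individual score is missing, and PASI uses 3 severity scores and 1 area score in each of 4 regions: 4 × 4 = 16 inputs. One blank input makes PASI missing, and rebound with it, even if sPGA has clearly worsened.

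**3. Patient level.** A re-randomized patient has PASI 90 at Week 16, so PASI is at most 10% of baseline and the PASI component is negative. If sPGA was also recorded, Week 16 is a non-missing visit and in practice reads *no*. The patient-level missing rule requires every visit from Week 16 to Week 28 to be missing, so it does not apply. Two kinds of patient are then coded *no*:

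- one whose only positive visit lacked sPGA or PASI;
- one with no visit after Week 16.

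The first stays in the denominator, so the error is misclassification rather than exclusion.

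**4. Size of a lost case, following Table AMAK.6.5.** Each one costs 1/93 = 1.1 points. With an assumed 2 true rebounds, one of them at a partly scored visit: 2/93 = 2.2% becomes 1/93 = 1.1%. With an assumed 4: 4/93 = 4.3% becomes 3/93 = 3.2%.

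**5. Size of the window effect.** Let x be observed rebounds and d patients with no data after Week 16, both assumed.

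| x | d | As written, x/93 | Post-Week-16 visits only, x/(93 − d) | Upper bound, (x + d)/93 |
|---|---|---|---|---|
| 1 | 2 | 1.1% | 1/91 = 1.1% | 3/93 = 3.2% |
| 3 | 5 | 3.2% | 3/88 = 3.4% | 8/93 = 8.6% |
| 5 | 9 | 5.4% | 5/84 = 6.0% | 14/93 = 15.1% |

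Correcting the denominator alone moves the rate little. The last column, which treats every unfollowed patient as a rebound, shows the uncertainty that coding them *no* conceals.

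**The case against.** The best case for leaving the text alone has four parts.

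**Scoring should be nearly complete.** PASI and sPGA are scheduled at every visit and at the early termination visit, which patients who stop treatment early are to attend. A reader might infer that patients with a phenotype change will tend to lack scores because Protocol Section 8.2 takes them off treatment; the documents do not say so, and a scored visit is due at that point. One fully scored positive visit in the window is also enough. This stands, and it keeps the expected number of cases small.

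**The as-observed analysis may already exclude early dropouts.** On the completers wording of Section 6.3.4, a patient lost after Week 16 would not be counted at all, and the definition's own qualifier points to events after re-randomization. Against this, the 12-week row names Week 16 in both its derivation and its missing rule, and takes any non-missing visit. The SAP does not say which governs. A strict completers reading would also remove a patient who rebounded and was withdrawn before Week 28, so it is no remedy.

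**Week 16 is not guaranteed to be non-missing.** A reader might conclude that the patient-level missing rule can never operate. That is too strong: re-randomization guarantees a Week 16 PASI but not an sPGA, and a missing sPGA makes that visit missing. The supportable word is normally.

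**Phenotype changes do not vanish from the report.** They lead to discontinuation, and SAP Section 6.6 tabulates and lists discontinuation reasons; Protocol Section 9.2 has changes in condition recorded as adverse events. Nor do the documents rank the three components, so it cannot be said that the cases lost are the most serious kind. This stands, but it does not correct the rebound rate itself.

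**Conclusion.** The point holds as a flaw in a stated derivation, with a small expected effect. Followed as written, Table AMAK.6.5 discards an observed positive component whenever sPGA or PASI is missing at that visit, and nothing else in the protocol or SAP overrides this. With the pre-dose Week 16 visit in the window, the affected patient, or one with no withdrawal follow-up, is normally reported as rebound-free unless another fully scored visit in the window is positive.

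Under that derivation each lost rebound costs about 1.1 percentage points on about 93 patients. It would be tempting to say that the lost case drops out of the summary and the denominator shrinks to 92; under Table AMAK.6.5 it does not, because the Week 16 visit keeps the patient in as a non-event.

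The rebound and dropout counts used here are assumptions. Rebound is an other-secondary, descriptive endpoint outside the multiplicity graph, so the primary and major secondary conclusions are unaffected.

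**What to change.** In Table AMAK.6.5:

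1. Code rebound at a visit *yes* if any observed component is met; *no* only if sPGA and PASI are both observed and no component is met; otherwise missing.
2. For the 12-week variable, count only visits after the Week 16 re-randomization and up to Week 28. Include an early termination visit only if it falls in that window, so that a late one cannot enter a 12-week endpoint.

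In Table AMAK.6.6 or Section 6.3.4:

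3. State the denominator for this endpoint and reconcile it with the completers wording.
4. Report separately the number of patients without follow-up to Week 28. A patient with one negative Week 20 visit and nothing later would still be coded *no*, and the reader needs to see how many there are.

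The cost is a few sentences in the SAP and a small change to the derivation program. No new data are needed. The change is best made before unblinded maintenance data are seen.
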